14.0 Withdrawal of Subjects*

14.1 Describe anticipated circumstances under which subjects will be withdrawn from the research without their consent.

Anticipated circumstances under which subjects will be withdrawn from the research without their consent include inattentiveness, damage to research equipment, clear misunderstanding of task instructions, and inappropriate behavior such as yelling or swearing.

14.2 Describe any procedures for orderly termination.

NA

14.3 Describe procedures that will be followed when subjects withdraw from the research, including partial withdrawal from procedures with continued data collection.

Procedures that will be followed when subjects withdraw from the research, including partial withdrawal from procedures with continued data collection, include appropriate compensation for their time and safekeeping of their data in appropriate records. Identifying information will be retained in digital format. Digital information will be stored on password protected local machines, or on secure cloud based services such as Google Docs also requiring a password.

15.0 Risks to Subjects*

15.1 List the reasonably foreseeable risks, discomforts, hazards, or inconveniences to the subjects related to the subjects' participation in the research. Include as may be useful for the IRB's consideration, a description of the probability, magnitude, duration, and reversibility of the risks. Consider physical, psychological, social, legal, and economic risks.

Risks for the study include:

GENERAL INFORMATION TMS is applied through a magnetic stimulator. This device consists of a set of electrical capacitors which can store and rapidly discharge electricity into a coil of electrical wire that is encased in shielded plastic. We will use MagPro X100 Magnetic Stimulator equipped for a figure 8 (i.e. butterfly) coil (MCF-B65) and a flex arm for coil positioning. The stimulator is manufactured by MagVenture, which is one of the most established manufacturers of TMS equipment with arguably the best currently available products and an excellent safety record. The coil is placed adjacent to the scalp above the targeted region. As the electrical current flows through the coil, a magnetic field is generated. The field passes through the skin and skull, inducing a brief change in the electrical flow of current in the brain. The magnetic pulse briefly alters neural activity in brain areas lying directly beneath the coil, presumably by causing discharge of neurons to a depth of 1.5 to 2.0

PROTOCOL TITLE: TMS Studies of Working Memory and Cognitive Control

cm below the scalp. TMS has been used in a large number of laboratories worldwide for over 30 years. When administered within documented safety guidelines, adverse effects associated with TMS are rare. The risk of such adverse effects depends greatly on the form of stimulation employed. Below, various risks and side effects are described with an account of the likelihood of each effect under the proposed stimulation conditions. The primary sources for this information come from the recommendations of the International Workshop on the Safety of Repetitive Magnetic Stimulation, June 57, 1996 (reported in Wassermann, 1998). A new set of guidelines was published in 2009 (Rossi et al., 2009) based on a consensus conference which took place in Certosa di Pontignano, Siena (Italy) in 2008. Our proposed studies fall firmly within these established safety guidelines. There are no known long-term health risks to the use of TMS per se when operated within consensus safety guidelines (Rossi et al., 2009). In 2008, the FDA approved the use of high frequency TMS in the treatment of depression. Also in 2008, an international consensus conference on safety guidelines for TMS met. Their report (Rossi et al., 2009) systematically reviewed the thousands of healthy subjects and patients who have undergone TMS in order to allow for a better assessment of relative risks. The relative infrequency of adverse events using TMS was noted. They concluded that in the case of Class 3 studies (studies involving indirect benefit and low risk in normal subjects and patients that are expected to yield important data on brain physiology or safety, but have no immediate relevance to clinical problems), normal volunteers should be permitted to participate in TMS research. They also concluded that this research can be performed in a nonmedical setting (i.e., psychology labs, robotics labs, research institutions, etc. as opposed to a hospital or appropriately equipped outpatient clinic). The Rossi et al. (2009) consensus report went on to suggest safety guidelines based on the now rather extensive international experience with TMS. These guidelines include the TMS intensity and timing parameters considered safe, training, and planning for and managing emergencies. We will follow these guidelines, and have incorporated them into our screening and session procedures. The consensus safety guidelines (Rossi et al., 2009) are included as a supporting document attachment with this IRB application.

The PI on this project ([name]) has extensive experience with TMS during both graduate school and post-doctoral studies. He received formal training in the administration of TMS through an intensive course offered by Harvard Medical School (<http://tmslab.org/educationintensive.php>) lead by [name], a world leader in non-invasive brain stimulation. He has delivered or directly supervised over 100 sessions of TMS with no serious adverse effects. Over the course of these sessions, one

PROTOCOL TITLE: TMS Studies of Working Memory and Cognitive Control

participant withdrew from the study due to discomfort in a muscle near the stimulation site, and another withdrew due to dizziness. No other side effects have been reported. It is important to note that TMS protocols in the literature differ with respect to stimulation intensity, frequency, and duration. Adverse effects increase as each of these variables increases. The TMS protocols to be used in this study are reflective of the PI's previous studies and are suggestive of a low incidence of adverse effects with the planned stimulation parameters. Here I list the documented risks associated with TMS: Seizure. Seizure is a theoretical risk with TMS. In a workshop convened by the National Institute for Neurological Disorders and Stroke (NINDS) in 1996, researchers in the field agreed upon a set of TMS consensus safety guidelines, including recommended stimulation parameters and contraindications (Wasserman, 1998), and these consensus guidelines have been recently updated (Rossi et al., 2009). Widespread adherence to the 1996 guidelines has resulted in the virtual elimination of inadvertent seizures in TMS studies (Rossi et al., 2009). The levels of stimulation used in this protocol are well within safety guidelines (Rossi et al., 2009; Wassermann et al. 1998). In the Rossi et al. (2009) report it was stated that "the occurrence of seizures has been extremely rare, with most of the few new cases receiving rTMS protocols exceeding previous guidelines, often in patients under treatment with drugs which potentially lowered the seizure threshold. A total of 16 seizure cases have been identified to date (from tens of thousands on participants tested). Seven of these cases were included in the previous 1998 safety guidelines and 9 had been reported subsequent to the 1996 report. The majority of the seizures were induced in studies 1) using parameters outside the safety guidelines 2) examining patients with neurological or psychiatric conditions taking pro-epileptogenic medications, or 3) both. Our protocol excludes patients taking pro-epileptogenic medications and uses stimulation parameters that are well within the safety guidelines (Rossi et al., 2009). Four of the new seizures (two following single-pulse and two following repetitive TMS, rTMS) appear to have been induced in studies using "safe" stimulation parameters. The two rTMS incidents involved patients with either major depression (Figiel et al., 1998) or tinnitus (Nowak et al., 2006). The single-pulse incidents involved a patient with multiple sclerosis (Haupts et al., 2004) and a patient with bipolar depression (Tharayil et al., 2005). In summary, all of the new seizure incidents involved patients that would be excluded by our protocol, and in three of the cases, the patients were TAKING proepileptogenic medications. Since 2009, only one more seizure has been reported (Katz et al., 2011). This occurred in a healthy subject who developed symptoms of a seizure after single pulse TMS during initial motor threshold estimation. The initial stimulation setting was


Local pain, headache, or discomfort. The most commonly reported side effect of TMS is headache. This headache is typically of a muscle-tension type. It usually develops during or immediately after the stimulation and may last for minutes to hours following the end of the stimulation. It is typically limited to the day of stimulation. Neck pain or scalp pain may also occur. Both are usually managed easily with over-the-counter analgesics. The experimental procedure will be immediately terminated whenever anyone reports

PROTOCOL TITLE: TMS Studies of Working Memory and Cognitive Control

experiencing discomfort. There are no reports of any such effects recurring. For many scalp locations, TMS feels only like a sudden tap on the scalp accompanied by a clicking sound. For other scalp locations, TMS can cause face or limb twitches. These twitches are not painful, but can feel odd or disquieting when first experienced. On some occasions, TMS might cross the threshold to the point where it would actually be described as producing a slightly painful scalp sensation. We will closely monitor subjects' comfort and will request them to tell us if the stimulation ever feels painful. If this occurs, we will immediately decrease TMS intensity to a level that is not painful. It is important to note that the likelihood of headache and other discomfort depends upon the stimulation parameters.

Parameters for clinical applications for depression note a rate of 28% for pain, which is greater than the 16% observed for sham (i.e. no true stimulation; Loo et al., 2008). However, for TBS, the rate is less than 3% (Oberman et al., 2011). In many cases, discomfort can be due to neck pain resulting from holding one's head still against the coil. The figure 8 coil (MCF-B65) is lightweight compared to most coils and will be supported by an arm for positioning that alleviates downward pressure on the subject. Therefore, we anticipate rates of adverse effects due to pain and discomfort will be low and in accordance with the PI's previous history with the technique.

Transient hearing changes. TMS produces an audible clicking noise when the current passes through the coil. This click can result in tinnitus and transient decreased hearing if no protection is used. To prevent this adverse effect, all experimental participants will wear ear plugs. Animal and human studies have demonstrated that earplugs can effectively prevent the risk of hearing disturbances or discomfort due to TMS.

Participants may experience lightheadedness or dizziness. In rare cases, a syncope may occur (Rossi et al., 2021). Participants will be verbally queried for any feelings of lightheadedness or dizziness immediately after stimulation. Since these symptoms typically result from cerebral hypoperfusion (i.e. reduced blood flow to the brain), steps will be taken to facilitate cerebral perfusion including hydration (offering the participant water), cold compress to reduce vasodilation, and lowering the head of the participant. The procedure chair can recline to facilitate the latter. In the event of dizziness, experimental procedures will be paused until symptoms resolve. In the rare event of a syncope, participants will be monitored until they regain consciousness. Experimental procedures will be terminated, and the IRB will be informed.

The experimenters will also be provided with ear protection devices to minimize any discomfort they might experience from the clicks. Transient cognitive/neuropsychological changes. Some repetitive TMS protocols have been shown to affect cognitive processing for

PROTOCOL TITLE: TMS Studies of Working Memory and Cognitive Control

up to one hour following stimulation. Specifically, this is the case for "offline" techniques such as 1 Hz stimulation and theta-burst stimulation (TBS; Huang et al., 2005). These changes are small, but could in theory affect the subject's ability to drive home safely. However, our use of offline TMS always precedes the actual experimental task that subjects are performing. Since the effects of the TMS parameters we are proposing to use have never been observed to last more than 1 hour, the potential cognitive effects of TMS are expected to have worn off by the time the testing session is concluded. Participants may experience frustration from poor performance on the task. Another potential risk is probing for personal or sensitive information in surveys, interviews, or questionnaire.

15.2 *If applicable, indicate which procedures may have risks to the subjects that are currently unforeseeable.*

NA

15.3 *If applicable, indicate which procedures may have risks to an embryo or fetus should the subject be or become pregnant.*

While the health risks to the fetus are unknown, magnetic field strength decreases approximately with the cube-root of the distance from the magnetic coil. Therefore, a coil located on the scalp will have little direct effect on the abdomen, though changes in neural firing or emotional stress levels could in theory have distal impact.

15.4 *If applicable, describe risks to others who are not subjects.*

NA

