motor threshold (AMT). 2) Observing a visually-identified hand twitch in the hand contralateral to TMS (e.g. if applying TMS to the left hemisphere of the brain, a twitch will be observed in the right hand). This is referred to as the resting motor threshold (RMT). In most cases, the AMT will be determined. However, if EMG cannot be recorded due to technical issues (e.g. the participant's hand is too sweaty to record a strong signal), RMT will be recorded. In both cases, the scalp region producing the largest hand twitch will be identified. To identify this region, TMS will be set to 30% of the maximal stimulator output, which is well below the motor threshold for most, if not all, individuals. TMS will be delivered to a scalp location approximating the location of motor cortex based upon surface features using the nose and ears as landmarks. From this initial location, TMS will be delivered. If ineffective to produce a hand twitch, the TMS coil will be moved to a new, nearby site, which will subsequently be tested. This process will continue until a grid of locations has been tested around the starting location, approximating 5 cm². If a hand twitch has not been produced, this indicates that the stimulation is below threshold and the stimulator output will be raised by 5% of the maximum stimulator output. The process will then repeat until the maximal hand twitch at a given stimulation level is observed, thereby indicating the location of interest. During this process, the participant will be closely monitored and periodically asked whether the stimulation is producing any discomfort or unusual symptoms (e.g. dizziness). At the scalp location of interest, the lowest TMS intensity able to elicit 5 visible cessations of EMG activity in 10 trials (AMT), or 5 visible twitches in 10 trials (RMT) at this site will be determined. Individual MT will be used to determine the intensity of stimulation for each individual, as recommended by safety guidelines. This procedure usually takes about 5 minutes and also serves the purpose of acquainting participants to TMS stimulation. Once MT is determined, TMS will be administered within the limits of the safety guidelines recently updated in Rossi et al., 2021. An additional 12 years of research using TBS ranging between 80% and 100% RMT was examined to determine the continued efficacy of previously established guidelines in Rossi et al., 2009. Since the 2009 publication, the scientific community has gained a better understanding of safety risks and the rarity of adverse events (such as seizure) associated with TMS. To reflect current safety guidelines for offline studies using TBS, TMS will never exceed 100% of RMT or 120% of AMT. For offline studies using 1Hz stimulation, TMS will never exceed 110% of RMT or 130% of AMT. For online studies, TMS will never exceed 110% of RMT or 130% of AMT. Electroencephalography (EEG) will be used to either guide TMS frequencies and/or targets, measure changes in brain activity

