9.0 Study Timelines*

9.1 Describe:

- *The duration of an individual subject's participation in the study.*
- *The duration anticipated to enroll all study subjects.*
- *The estimated date for the investigators to complete this study (complete primary analyses)*

The duration for each individual's participation will be between 1 and 2 hours per session. Participants will participate in at least 1, and potentially several sessions. It may take up to several weeks to complete an entire task. The duration anticipated to enroll all study subjects is 72 months.

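### Session end does not guarantee the one-hour interval after offline TMS that section 15.1 relies on before participants drive home

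*Combined protocol and SAP*

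**What the plan says.** Section 15.1, under transient cognitive changes, says that 1 Hz stimulation and theta-burst stimulation can affect cognitive processing for "up to one hour following stimulation". It describes the changes as small but accepts that they could in theory affect a participant's "ability to drive home safely".

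Its answer has two parts. The first is order: "our use of offline TMS always precedes the actual experimental task that subjects are performing". The second is duration: "Since the effects of the TMS parameters we are proposing to use have never been observed to last more than 1 hour", it concludes that "the potential cognitive effects of TMS are expected to have worn off by the time the testing session is concluded".

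On session length, section 9.1 states: "The duration for each individual's participation will be between 1 and 2 hours per session". Section 1.0 gives the same 1 to 2 hours. Section 6.2 allows tasks as short as 5 to 10 minutes. Neither section ties a session length to a type of stimulation.

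The nearest related safeguard, also in section 15.1, is a query about lightheadedness immediately after stimulation, with this rule: "In the event of dizziness, experimental procedures will be paused until symptoms resolve". The protocol text has no minimum wait after stimulation and no driving advice.

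**The concern.** The protocol raises driving safety itself and then rests it on the session being over. What matters is the time since stimulation ended, and nothing in the plan controls that time. Stimulating before the task secures the hour only if the task and whatever follows it last an hour. Neither the session range nor the task range requires this.

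Early stopping is a second route to the same gap. Procedures end when a participant reports discomfort (section 6.3), participants may be withdrawn for inattentiveness (section 14.1), and they may leave whenever they wish (section 19.2). Any of these can put someone on the road inside the hour, even from a session scheduled for two hours.

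The dizziness query does not fill the gap. It asks about symptoms just after stimulation, not about elapsed time or subtle cognitive change. The participants are healthy volunteers with no direct benefit (section 16.0), so a foreseeable risk that the protocol names should have a safeguard that works in every session it permits.

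**Working it through.** **Inputs**

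- Longest effect after stimulation: 60 min (section 15.1). This is the protocol's reading of the literature and cannot be recomputed here.
- Session length: 60 to 120 min (section 9.1).
- Motor-threshold finding, before stimulation: "This procedure usually takes about 5 minutes" (section 6.1).
- Continuous TBS: 600 pulses in 3-pulse bursts at 5 bursts per second (section 6.1), so 600 / 3 / 5 = 40 s = 0.67 min.
- Intermittent TBS: 190 s = 3.17 min (section 6.1). Check: each 2 s train holds 10 bursts, or 30 pulses; 600 / 30 = 20 trains; 19 × 10 s + 2 s = 192 s, which agrees with the stated figure to within 2 s.
- 1 Hz: at most 30 min (section 6.1). Trains of 10 and 20 min are my illustrative assumptions.
- Set-up before stimulation: 5 min (threshold finding only). The assumed bounds are 0 min and, if consent, re-screening and EEG preparation count as session time, 25 min.

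**Formulas**

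Time after stimulation = session length − set-up − stimulation.

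Shortfall = 60 − time after stimulation. In a 60-minute session this equals set-up + stimulation, so it is above zero for every offline method.

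**Shortfall in a 60-minute session (min)**

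| Set-up | Continuous TBS | Intermittent TBS | 1 Hz, 10 min | 1 Hz, 20 min | 1 Hz, 30 min |
|---|---|---|---|---|---|
| 0 | 0.7 | 3.2 | 10 | 20 | 30 |
| 5 | 5.7 | 8.2 | 15 | 25 | 35 |
| 25 | 25.7 | 28.2 | 35 | 45 | 55 |

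At 5 min of set-up, the time left after stimulation is 54.3, 51.8, 45, 35 and 25 min.

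**Session length that clears the hour = 60 + set-up + stimulation (min)**

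| Set-up | Continuous TBS | Intermittent TBS | 1 Hz, 10 min | 1 Hz, 20 min | 1 Hz, 30 min |
|---|---|---|---|---|---|
| 0 | 60.7 | 63.2 | 70 | 80 | 90 |
| 5 | 65.7 | 68.2 | 75 | 85 | 95 |
| 25 | 85.7 | 88.2 | 95 | 105 | 115 |

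A 90-minute session with 5 min of set-up clears TBS easily, but leaves 90 − 5 − 30 = 55 min after a full 1 Hz train, 5 min short. Every entry in the second table is below 120 min, so a completed session near the upper limit clears the hour if stimulation comes early.

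**The case against.** The arithmetic is hard to dispute, so the case against concerns how far it reaches.

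- **The consent document may already advise on driving.** Such advice often belongs there, and section 23.3 says a consent document is attached. It could not be reviewed. This stands as a limit on what can be said about participants' overall protection, but the reasoning in section 15.1 would still need correcting.
- **The testing session might mean only the task after stimulation.** A task of an hour or more would then meet the bound. This reading is weak: section 9.1 counts the individual's participation, and section 6.2 allows tasks of 5 to 10 minutes.
- **The largest shortfalls come from awkward sessions.** A 60-minute session with 25 min of set-up and 30 min of 1 Hz leaves 5 min for the task, the shortest length allowed. That stands: the bottom row of the first table shows permitted cases, not expected ones, and its longer 1 Hz entries are improbable.
- **For TBS the gap is minutes, against an upper bound.** That also stands. Rinsing out EEG gel after participation (section 6.1) may cover it. It is unlikely to cover 35 min after 1 Hz.
- **Stopping is not the same as leaving.** The plan also provides for breaks, lower intensity and pauses, and does not say that a participant leaves at once when procedures stop. But section 19.2 lets participants leave at any moment.
- **The frequency of early stops is unknown.** Section 15.1 reports two withdrawals, for muscle discomfort and dizziness, in over 100 earlier sessions. These show that early stops happen. They give no rate for this study, because other reasons for stopping are not counted and the stimulation type is not stated.

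**Conclusion.** The concern holds, as a minor participant-safety point. In a permitted 60-minute session with 5 min of threshold finding, the participant finishes 5.7 min (continuous TBS), 8.2 min (intermittent TBS) or up to 35 min (1 Hz) before the protocol's own hour has passed. The shortfall remains above zero with no set-up at all.

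This rests on stimulation falling inside the session and on the one-hour bound in section 15.1. It applies to offline TMS only. It shows that the stated safeguard does not assure clearance, not that impairment persists or that anyone is harmed. The cases that matter most are long 1 Hz trains in short sessions and sessions stopped early.

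**What to change.** In section 6.2, for offline sessions, add that staff record the time stimulation ends, ask the participant to remain until 60 minutes after it, and advise anyone leaving sooner, for any reason, not to drive until that time. Reword section 15.1 to rest on this interval instead of on session end. If the consent document already gives driving advice, cite it there.

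The wording cost is two or three sentences. With 5 min of set-up in a 60-minute session, the added wait at the protocol's $15 per hour costs 5.67 / 60 × 15 = $1.42 per paid participant after continuous TBS, 8.17 / 60 × 15 = $2.04 after intermittent TBS, and at most 35 / 60 × 15 = $8.75 after 1 Hz, or the same time in course credit. In the extreme 55-minute case it is 55 / 60 × 15 = $13.75. Staff and room time are extra.

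Scheduling can remove most of the wait: even 25 + 30 + 60 = 115 min fits the permitted two hours. The drawback is that the shortest offline sessions become longer. Participants remain free to go, so the driving advice is the part that protects those who leave early.
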